5.7.9 Re-planning

Re-planning (such as to account for changes in tumor volume) is allowed. If re-planning is necessary, the new treatment plan should meet the same criteria as the initial plan, as if the new plan were delivered for the entire treatment course. The new treatment plan should be submitted for central review according to the same process as the initial plan.

6 DOSING DELAYS/DOSE MODIFICATIONS CISPLATIN/RADIATION

6.1 Prior to dosing with cisplatin any day, the following criteria must be met (please refer to Nivolumab requirements to dose as well if dosing on applicable day is for both drugs):

- ANC \geq 1000/mcl
- Platelet count \geq 50,000/mcl

*If patient experienced a ANC < 1,000 or a PLT count < 50,000 consider drawing CBC twice weekly (not required)

BrUOG 355: 7/8/17, 7/11/17, 7/20/17, 8/7/17, 8/8/17, 8/14/17, 8/16/17, 8/21/17, 8/22/17, 8/24/17, 8/28/17, 9/5/17, 9/6/17, 9/8/17, 9/11/17, 11/7/17, 11/8/17, 11/19/17 approved DD, 11/20/17, 12/12/17, 12/14/17, 1/29/18, 2/1/18, 2/6/18, 2/7/18, 2/8/18, 2/9/18, 2/12/18, 2/13/18, 3/8/18 all reviews, 3/9/18, 3/13/18, 3/14/18, 3/15/18, 4/19/18, 4/23/18, 5/29/18, 6/5/18, Amendment # 1 7/9/18, Amendment # 2 12/12/18, Amendment #3, 4/6/2020, Amendment #4 5/11/2020

The following table will be used for dose adjustment:

Cisplatin dosing table

Starting dose all patients	Dose -1	Dose -2
40 mg/m ² (maximum 70mg/week BSA 1.75m ²)	30 mg/m ² (maximum 60mg/week)	25mg/m ² (maximum 50mg/week)

*All dose reductions are permanent and each patient can only have 2 dose reductions before needing to come off study

For all patients undergoing chemoradiation, all non-hematological related toxicities must be \leq grade 2 to continue with cisplatin, with the following notes:

- Hold chemoradiation for GI toxicities (including diarrhea, nausea, vomiting) \geq grade 3, may resume only when \leq grade 1
- Creatinine \leq 2.0mg/dL
 If it is $>$ 2.0mg/dL draw CrCl and consider renal ultrasound.
 If CrCl is \geq 50 ml/min, continue therapy.
 If CrCl is \leq 50 ml/min, hold treatment and check CrCl weekly.
 When the CrCl is \geq 50 ml/min, or the serum creatinine \leq 2.0 mg/dl, resume therapy at one dose level reduction.
 Persistence of CrCl \leq 50 ml/min or serum creatinine \geq 2.0 mg/dl for $>$ two weeks patient's study therapy with Nivolumab will be stopped. However, patients will continue on definitive chemoradiation as standard of care, off protocol, as directed by their treating physician.
- Neurotoxicity (including neuropathy and paresthesia) \leq grade 2
 If patient experiences a grade 3-4 neurotoxicity patient will be removed from study

Refer to section 7 for more information on supportive care

In situations when RT is not given (held for toxicity or other reasons (weather, machine is down, holiday), cisplatin and Nivolumab should not be given and should also be held.

If Nivolumab is held on a day Cisplatin is due and the patient meets criteria to receive Cisplatin and Radiation then every attempt should be made to administer Cisplatin and radiation, while holding Nivolumab.

Every attempt should be made for all patients to complete radiation therapy (even if cisplatin and nivolumab are held)

6.2 Radiation therapy:

Prior to Radiation administration a patient must be confirmed as having:

BrUOG 355: 7/8/17, 7/11/17, 7/20/17, 8/7/17, 8/8/17, 8/14/17, 8/16/17, 8/21/17, 8/22/17, 8/24/17, 8/28/17, 9/5/17, 9/6/17, 9/8/17, 9/11/17, 11/7/17, 11/8/17, 11/19/17 approved DD, 11/20/17, 12/12/17, 12/14/17, 1/29/18, 2/1/18, 2/6/18, 2/7/18, 2/8/18, 2/9/18, 2/12/18, 2/13/18, 3/8/18 all reviews, 3/9/18, 3/13/18, 3/14/18, 3/15/18, 4/19/18, 4/23/18, 5/29/18, 6/5/18, Amendment # 1 7/9/18, Amendment # 2 12/12/18, Amendment #3, 4/6/2020, Amendment #4 5/11/2020

- ANC > 500/mcl
- Platelets > 50,000/mcl
- GI toxicities \leq grade 2
- Bladder toxicities \leq grade 2

Radiation therapy will not be interrupted for uncomplicated hematological toxicity. For purposes of this trial, complicated hematologic toxicity is defined as:

- Grade 4 neutropenia- hold radiation until neutropenia is grade 3 or less
Grade 3-4 thrombocytopenia, hold radiation until thrombocytopenia is grade 2 or less
RT should be held until ANC > 500/mcl and platelets > 50,000/mcl. Radiation should then be restarted, even if cisplatin (and nivolumab) are held.

An uncomplicated hematological toxicity is any hematological toxicity that does not meet the above criteria.

Refer to section 7 for more information on supportive care

Other toxicities:

RT should be held for \geq grade 3 GI toxicities (including diarrhea, nausea, vomiting).

Every attempt should be made for all patients to complete radiation therapy (even if cisplatin and nivolumab are held). Patient who require a hold of RT due to toxicity for 7 consecutive days or longer will be removed from protocol. See 5.7.1 for definition of deviations for RT delays.

In situations when RT is not given (held for toxicity or other reasons (weather, machine is down, holiday), cisplatin and Nivolumab should not be given and should also be held.

If Nivolumab is held on a day Cisplatin is due and the patient meets criteria to receive Cisplatin and Radiation then every attempt should be made to administer Cisplatin and radiation, while holding Nivolumab.

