5.6 Definitive Chemoradiation Plan

Standard therapy guidelines for definitive chemoradiation in cervical cancer will be utilized during this trial. All patients will receive tailored pelvic (if para-aortic nodes are negative) and/or extended field, pelvis+para-aortic, radiation therapy (if para-aortic nodes are involved) with a plan for daily delivery of RT (Monday-Friday) for approximately 6 weeks (which may include brachytherapy).

Cisplatin:

40 mg/m² of cisplatin (maximum total dose of 70 mg/week and maximum BSA=1.75m²)

Dosing on Days: 1, 8, 15, 22, 29, 36 (preferably on Mondays or Tuesdays). The only exception allowed is to account for holidays or unexpected events that warrant closure of the radiation oncology or infusion center, in which case treatment is allowed within the next fully operational day. For example, if D8 falls on a holiday, treatment with cisplatin (and with nivolumab if scheduled) should occur on next day, which will be counted as D8 with all subsequent days rescheduled to allow for a 7-day interval between dosing.

- Cisplatin should be infused **over approximately 1 hour**, beginning on day 1 of radiation therapy.

One hour before cisplatin administration, 500-1000 ml of normal saline should be infused intravenously, as per institutional standard of care.

Appropriate antiemetics should be administered prior to cisplatin. Additional fluid may be given as needed for symptomatic support. Premedications for nausea and vomiting prophylaxis should follow institutional guidelines.

Immediately after completion of the cisplatin infusion, an additional 500-1000 ml normal saline should be infused over one hour. It is highly recommended that KCl 20-40 meq and MgSO₄ 2 grams be added to the normal saline in the post hydration fluid given that hypomagnesemia and

BrUOG 355: 7/8/17, 7/11/17, 7/20/17, 8/7/17, 8/8/17, 8/14/17, 8/16/17, 8/21/17, 8/22/17, 8/24/17, 8/28/17, 9/5/17, 9/6/17, 9/8/17, 9/11/17, 11/7/17, 11/8/17, 11/19/17 approved DD, 11/20/17, 12/12/17, 12/14/17, 1/29/18, 2/1/18, 2/6/18, 2/7/18, 2/8/18, 2/9/18, 2/12/18, 2/13/18, 3/8/18 all reviews, 3/9/18, 3/13/18, 3/14/18, 3/15/18, 4/19/18, 4/23/18, 5/29/18, 6/5/18, Amendment # 1 7/9/18, Amendment # 2 12/12/18, Amendment #3, 4/6/2020, Amendment #4 5/11/2020

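### The cisplatin weekly caps rest on two different body surface areas (1.75 m² at the starting dose, 2.0 m² at both reduced levels), and the protocol does not say whether its 1.75 m² limit holds after a dose reduction

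*Combined protocol and SAP*

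**What the plan says.** Section 5.6 sets weekly cisplatin at 40 mg/m² with two limits side by side: a "maximum total dose of 70 mg/week and maximum BSA=1.75m²".

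Section 6.1 introduces its dosing table with "The following table will be used for dose adjustment". The table has three columns:

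- Starting dose, 40 mg/m²: "maximum 70mg/week BSA 1.75m ²".
- Level -1, 30 mg/m²: "maximum 60mg/week", with no BSA limit.
- Level -2, 25 mg/m²: "maximum 50mg/week", with no BSA limit.

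A note under the table adds: "All dose reductions are permanent and each patient can only have 2 dose reductions before needing to come off study". For renal toxicity, sections 6.1 and 7.1.3 both have treatment resume one dose level lower.

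No section says whether the 1.75 m² limit carries over to the two reduced levels.

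**The concern.** At the starting dose the milligram cap and the BSA limit are the same limit expressed in two ways. At the reduced levels they cannot be, because 60 and 50 mg do not correspond to 1.75 m². A site treating a patient above 1.75 m² must therefore choose between carrying the BSA limit forward and using the printed cap alone. The two choices give different doses.

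The question arises only after a reduction, which is when the dose given matters most for tolerance. Reductions are permanent and limited to two. Acute toxicity is the primary endpoint in section 16.1. Cohort feasibility in section 16.1.1 turns on more than 2 of 8 or more than 1 of 4 patients having a persistent grade 3 or higher event, or failing to finish chemoradiation within 8 weeks. In cohorts of that size, the regimen actually delivered should not depend on how a site reads a table.

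**Working it through.** **Inputs.** Dose levels of 40, 30 and 25 mg/m² and weekly caps of 70, 60 and 50 mg come from the section 6.1 table. The maximum BSA of 1.75 m² comes from section 5.6 and the first column of that table.

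**Step 1: reproduce the plan's own cap.** Cap = dose per m² × maximum BSA. At the starting dose, 40 × 1.75 = 70 mg, which matches the printed figure.

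**Step 2: BSA implied by each cap.** Implied BSA = cap ÷ dose per m².

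- Starting dose: 70 / 40 = 1.75 m²
- Level -1: 60 / 30 = 2.0 m²
- Level -2: 50 / 25 = 2.0 m²

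**Step 3: highest dose if the 1.75 m² limit applies throughout.**

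- Level -1: 30 × 1.75 = 52.5 mg, below the printed 60 mg
- Level -2: 25 × 1.75 = 43.75 mg, below the printed 50 mg

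On this reading neither printed cap is ever reached.

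**Step 4: delivered dose under each reading.** Reading A uses the milligram caps alone: dose = min(mg/m² × BSA, cap). Reading B also holds BSA at 1.75 m² at every level. Percentages are reductions from the patient's own starting dose.

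| BSA (m²) | A: start → -1 → -2 (mg) | A: reduction | B: start → -1 → -2 (mg) | B: reduction |
|---|---|---|---|---|
| 1.75 | 70 → 52.5 → 43.75 | 25.0% / 37.5% | 70 → 52.5 → 43.75 | 25.0% / 37.5% |
| 1.80 | 70 → 54 → 45 | 22.9% / 35.7% | 70 → 52.5 → 43.75 | 25.0% / 37.5% |
| 1.90 | 70 → 57 → 47.5 | 18.6% / 32.1% | 70 → 52.5 → 43.75 | 25.0% / 37.5% |
| 2.00 or more | 70 → 60 → 50 | 14.3% / 28.6% | 70 → 52.5 → 43.75 | 25.0% / 37.5% |

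Below 1.75 m² the readings coincide, with reductions of 25.0% and 37.5%. The protocol states no percentages; these follow from 1 − 30/40 and 1 − 25/40.

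**Step 5: gap between readings at BSA 2.0 m² or more.**

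- Level -1: 60 − 52.5 = 7.5 mg per week; 7.5 / 52.5 = 14.3%
- Level -2: 50 − 43.75 = 6.25 mg per week; 6.25 / 43.75 = 14.3%

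**Step 6: dose per actual m² under reading A.**

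- BSA 1.9: start 70 / 1.9 = 36.8; level -1 57 / 1.9 = 30; level -2 47.5 / 1.9 = 25 mg/m²
- BSA 2.0: start 70 / 2.0 = 35; level -1 60 / 2.0 = 30; level -2 50 / 2.0 = 25 mg/m²

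Above 2.0 m² the caps bind and the reduced doses fall below 30 and 25 mg/m². No patient exceeds the stated level.

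**The case against.** The strongest reply is that there need be no arithmetic error. In both sections the 1.75 m² figure stands only beside the 40 mg/m² dose. It may simply explain the 70 mg cap, with 60 and 50 mg as separate round limits; different caps need not share one BSA. This reading is possible and the documents do not exclude it. They do not state it either, and section 5.6 gives the maximum BSA without confining it to the first dose level. What is established is therefore an unstated scope that leads to two different doses, and no more than that.

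A reader might infer that larger patients do receive too small a reduction, so that a step taken for toxicity is partly undone. The documents do not support this, for two reasons. It arises only under reading A; under reading B every patient gets the full 25% and 37.5%. Even under reading A, larger patients reach the stated 30 and 25 mg/m² or less. Their percentage step is smaller because their starting dose was already capped below 40 mg/m². Whether percentage of milligrams or dose per m² is the right measure of a reduction is a clinical judgement that the protocol does not make.

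It is also fair to say that an effect on the trial's results is not shown. The documents give no BSA distribution and no expected frequency of reductions. The only rule that explicitly calls for a one-level reduction is the renal one; the GI rule holds treatment and the neurotoxicity rule removes the patient.

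**Conclusion.** The inconsistency is real but limited. The starting cap rests on 1.75 m² and both reduced-level caps on 2.0 m², and the protocol does not say whether the 1.75 m² limit applies after a reduction. The consequence is conditional. If the limit applies, the printed 60 and 50 mg caps are redundant. If it does not, the steps at BSA of 2.0 m² or more are 14.3% and 28.6% in place of 25% and 37.5%.

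The difference in delivered dose between the readings is at most 7.5 mg per week at level -1 and 6.25 mg at level -2. It narrows to 1.5 mg (54 − 52.5) and 1.25 mg (45 − 43.75) at BSA 1.80 m², and is zero at or below 1.75 m². Only patients who are above 1.75 m² and also need a reduction are affected; how many of the planned 24 that would be cannot be derived from the documents. No overdose against the stated mg/m² and no bias in the toxicity endpoint is demonstrated. The point deserves correction because the table governs dosing after toxicity and currently permits two different doses for the same patient.

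**What to change.** Reconcile the section 6.1 table with section 5.6, and state in the table whether the maximum BSA applies at every dose level or only at the starting dose. If it applies throughout, the two reduced-level caps need to be made consistent with it. If it does not, one clause should say so. Which limit and which caps are right is a clinical decision for the sponsor, and none is proposed here.

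The cost is one clause or two numbers in a table, made through the protocol's usual amendment route. Sample size, endpoints and analyses are unchanged.

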7 RESCUE MEDICATIONS AND SUPPORTIVE CARE

7.1 Supportive Care Guidelines

Subjects should receive appropriate supportive care measures as deemed necessary by the treating investigator. Suggested supportive care measures for the management of adverse events with potential immunologic etiology are outlined below.

Where appropriate, these guidelines include the use of oral or intravenous treatment with corticosteroids as well as additional anti-inflammatory agents if symptoms do not improve with administration of corticosteroids. Note that several courses of steroid tapering may be necessary

BrUOG 355: 7/8/17, 7/11/17, 7/20/17, 8/7/17, 8/8/17, 8/14/17, 8/16/17, 8/21/17, 8/22/17, 8/24/17, 8/28/17, 9/5/17, 9/6/17, 9/8/17, 9/11/17, 11/7/17, 11/8/17, 11/19/17 approved DD, 11/20/17, 12/12/17, 12/14/17, 1/29/18, 2/1/18, 2/6/18, 2/7/18, 2/8/18, 2/9/18, 2/12/18, 2/13/18, 3/8/18 all reviews, 3/9/18, 3/13/18, 3/14/18, 3/15/18, 4/19/18, 4/23/18, 5/29/18, 6/5/18, Amendment # 1 7/9/18, Amendment # 2 12/12/18, Amendment #3, 4/6/2020, Amendment #4 5/11/2020

as symptoms may worsen when the steroid dose is decreased. For each disorder, attempts should be made to rule out other causes such as metastatic disease or bacterial or viral infection, which might require additional supportive care. The treatment guidelines are recommended when the investigator determines the events to be related to nivolumab.

It may be necessary to perform conditional procedures such as bronchoscopy, endoscopy, or skin photography as part of evaluation of the event. These procedures should be performed at the discretion of the investigator and are not mandated by the protocol.

7.1.1. Diarrhea/Colitis

Subjects should be carefully monitored for signs and symptoms of enterocolitis (such as diarrhea, abdominal pain, blood or mucus in stool, with or without fever) and of bowel perforation (such as peritoneal signs and ileus).

- For patients who are being treated with nivolumab **during** chemoradiation:
 - If diarrhea/colitis occurs **prior to** initiation of nivolumab or can be attributed to chemoradiation, then subjects should be advised to drink liberal quantities of clear fluids and will receive standard management for diarrhea with loperamide, low residue diet and Lomotil if needed. If sufficient oral fluid intake is not feasible, fluid and electrolytes should be substituted via IV infusion. For Grade 2 or higher diarrhea, consider GI consultation and endoscopy to confirm or rule out colitis.
 - If diarrhea/colitis occurs **after** subject has received any administration of nivolumab, then it is critically important to evaluate the subject for immune-related diarrhea/ colitis. The diarrhea/colitis is likely to be immune-related if it has any of the following characteristics:
 - Bloody or mucous stools
 - Cramping occurs at a timepoint not typical for chemoRT (i.e., in first 2 weeks of treatment or after completion of external beam RT)
- If the event meets these criteria (immune mediated), then it should be treated as follows:
 - All subjects who experience diarrhea/colitis should be advised to drink liberal quantities of clear fluids. If sufficient oral fluid intake is not feasible, fluid and electrolytes should be substituted via IV infusion.
 - For Grade 2 diarrhea/colitis that is felt to be possibly, probably, or likely related to nivolumab, administer oral corticosteroids consistent with Appendix D (GI Adverse Event Management Algorithm). Delay treatment as per

BrUOG 355: 7/8/17, 7/11/17, 7/20/17, 8/7/17, 8/8/17, 8/14/17, 8/16/17, 8/21/17, 8/22/17, 8/24/17, 8/28/17, 9/5/17, 9/6/17, 9/8/17, 9/11/17, 11/7/17, 11/8/17, 11/19/17 approved DD, 11/20/17, 12/12/17, 12/14/17, 1/29/18, 2/1/18, 2/6/18, 2/7/18, 2/8/18, 2/9/18, 2/12/18, 2/13/18, 3/8/18 all reviews, 3/9/18, 3/13/18, 3/14/18, 3/15/18, 4/19/18, 4/23/18, 5/29/18, 6/5/18, Amendment # 1 7/9/18, Amendment # 2 12/12/18, Amendment #3, 4/6/2020, Amendment #4 5/11/2020

appendix D.

- For Grade 3 diarrhea/colitis that is felt to be possibly, probably, or likely related to nivolumab and that persists > 1 week, treat with 1-2 mg/kg/day methylprednisolone IV (or equivalent). Discontinue nivolumab permanently. If opportunistic infection suspected, begin antibiotics promptly. If warranted, consider lower endoscopy. If improves, continue steroids until grade 1 then taper over at least a month, pending symptoms. If symptoms persist up to 5 days later, add infliximab 5 mg/kg (if no contraindication).
- For Grade 4 diarrhea/colitis, treat with 1-2 mg/kg/day methylprednisolone IV (or equivalent). Discontinue nivolumab permanently. If opportunistic infection suspected, begin antibiotics promptly.

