Immune mediated: Adverse events (both serious and non-serious) associated with nivolumab may represent immunologic etiology. Nivolumab must be held for suspected immune-mediated toxicities or severe/life-threatening AEs of particular interest (in Section 7.0) and immune-related toxicities (in Appendix D). Please review both Sections (7 and Appendix D) prior to infusion of nivolumab in any patient in whom immune-mediated toxicity is suspected.

If the investigator is unsure if a particular toxicity at least possibly represents an immune mediated toxicity to nivolumab, the treating physician should follow section 7 and appendix D and treat as immune mediated, until it is confirmed as not being immune mediated. Consultation with BrUOG is suggested in such situations. BrUOG will share information about the situation with the BrUOG Reviewer and PI and provide the site guidance, as available.

Removal from study (all cohorts):

Patients must discontinue nivolumab permanently for the following:

- Any Grade 2 drug-related uveitis or eye pain or blurred vision that does not respond to topical therapy and does not improve to Grade 1 severity within the re-treatment period OR requires systemic treatment
- Grade 3 drug-related thrombocytopenia > 7 days or associated with bleeding
- Any treatment delay resulting in no nivolumab dosing for > 6 weeks.
- Patients who discontinue nivolumab during definitive chemoradiation (cohorts one and three)
- Grade 4 drug-related endocrinopathy adverse events such as adrenal insufficiency, ACTH deficiency, hyper- or hypothyroidism, or glucose intolerance, hypophysitis.
- \geq Grade 4 hepatic AEs
- \geq Grade 4 skin toxicity (per Appendix D can delay or discontinue for grade 3. Must come off, as per this bullet for grade 4 skin)
- ALL OTHER treatment related grade 3/4 treatment related events with the following exceptions:
 - Grade 4 neutropenia \leq 7 days;
 - Grade 4 lymphopenia or leukopenia;
 - isolated Grade 4 electrolyte imbalances/abnormalities that are not associated with clinical sequelae and are corrected with supplementation/appropriate management within 72 hours of their onset;
 - Grade 3 hepatic AEs that return to Grade 2 or less within 5 days Of note, this overrides Appendix D
 - Skin toxicity \leq grade 3 that improves with steroid therapy. NOTE: Any rash consistent with Stevens-Johnson Syndrome or Toxic Epidermal Necrolysis requires permanent discontinuation of nivolumab.
 - Grade 3 renal toxicity (as per Appendix D)

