7.2 Criteria for Taking a Participant Off Protocol Therapy

Duration of therapy will depend on individual response, evidence of disease progression and tolerance. For patients receiving nivolumab during chemoradiation, treatment with nivolumab must be held if cisplatin is also held.

In the absence of treatment delays due to adverse event(s), treatment with nivolumab may continue as indicated in each cohort or until one of the following criteria applies:

- Disease progression
- Intercurrent illness that prevents further administration of treatment
- Unacceptable adverse event(s)
- Participant demonstrates non-compliance with treatment regimen and/or required study evaluations
- Participant decides to withdraw from the protocol therapy
- General or specific changes in the participant's condition render the participant unacceptable for further treatment in the judgment of the treating investigator
- Any required toxicity reason as noted in prior sections of the protocol requiring the

BrUOG 355: 7/8/17, 7/11/17, 7/20/17, 8/7/17, 8/8/17, 8/14/17, 8/16/17, 8/21/17, 8/22/17, 8/24/17, 8/28/17, 9/5/17, 9/6/17, 9/8/17, 9/11/17, 11/7/17, 11/8/17, 11/19/17 approved DD, 11/20/17, 12/12/17, 12/14/17, 1/29/18, 2/1/18, 2/6/18, 2/7/18, 2/8/18, 2/9/18, 2/12/18, 2/13/18, 3/8/18 all reviews, 3/9/18, 3/13/18, 3/14/18, 3/15/18, 4/19/18, 4/23/18, 5/29/18, 6/5/18, Amendment # 1 7/9/18, Amendment # 2 12/12/18, Amendment #3, 4/6/2020, Amendment #4 5/11/2020

- patient stop treatment
- Any adverse event, laboratory abnormality, or intercurrent illness which, in the judgment of the Investigator, presents a substantial clinical risk to the subject with continued nivolumab dosing

Participants will be removed from the protocol therapy when any of these criteria apply. The reason for removal from protocol therapy, and the date the participant was removed, must be documented in the case report form (CRF). Alternative care options will be discussed with the participant.

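### Section 7.1.1 ties permanent nivolumab discontinuation for related grade 3 diarrhoea/colitis to persistence beyond 1 week, whereas 5.5.1 requires it at any duration

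*Combined protocol and SAP*

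**What the plan says.** **Section 5.5.1, removal from study (all cohorts).** The list opens with "Patients must discontinue nivolumab permanently for the following". Its catch-all item is "ALL OTHER treatment related grade 3/4 treatment related events with the following exceptions". The exceptions that follow cover neutropenia, lymphopenia or leukopenia, electrolytes, hepatic events, skin and renal toxicity. Once nivolumab is discontinued, the patient comes off study.

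**Section 5.5.1, immune-mediated events.** Nivolumab is held for suspected immune toxicity, and staff are told: "Please review both Sections (7 and Appendix D) prior to infusion of nivolumab in any patient in whom immune-mediated toxicity is suspected". Where the cause is uncertain, "the treating physician should follow section 7 and appendix D and treat as immune mediated".

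**Section 7.1.1, diarrhoea/colitis.** The grade 3 bullet begins "For Grade 3 diarrhea/colitis that is felt to be possibly, probably, or likely related to nivolumab and that persists > 1 week". It then gives IV methylprednisolone and permanent discontinuation. The next bullet has no duration condition: "For Grade 4 diarrhea/colitis, treat with 1-2 mg/kg/day methylprednisolone IV (or equivalent). Discontinue nivolumab permanently".

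**Status of section 7.** Section 7.1 introduces its content this way: "Suggested supportive care measures for the management of adverse events with potential immunologic etiology are outlined below". Section 7.2 lists among the grounds for stopping protocol therapy "Any required toxicity reason as noted in prior sections of the protocol".

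**The concern.** A physician with a patient who has grade 3 diarrhoea after nivolumab is sent by 5.5.1 to section 7. There the instruction to stop for good carries a 1-week threshold at grade 3 and none at grade 4. The contrast invites the inference that a grade 3 episode settling within a week does not end nivolumab treatment. Under 5.5.1 it does, and the patient also leaves the study.

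At stake is a dosing error in a safety pilot: a further dose of a checkpoint inhibitor after a grade 3 episode for which the mandatory rule requires a permanent stop. Section 8.1 names diarrhoea/colitis among the select adverse events for nivolumab. In cohorts 2 and 3 maintenance is planned for 2 years, so many doses may remain after an early episode.

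**Working it through.** There is no sample size, power or event figure to reproduce. The check sets the two rules side by side and then looks for a statement of precedence.

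**1. Exceptions to the 5.5.1 catch-all.**

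| Exception | Time limit | GI event? |
|---|---|---|
| Grade 4 neutropenia | 7 days or less | No |
| Grade 4 lymphopenia or leukopenia | None | No |
| Isolated grade 4 electrolyte abnormality without sequelae | Corrected within 72 hours | No |
| Grade 3 hepatic | Back to grade 2 or less within 5 days | No |
| Skin, grade 3 or less, improving on steroids | None | No |
| Grade 3 renal | None (refers to Appendix D) | No |

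There are six exceptions, three with a time limit and none gastrointestinal. The catch-all itself has no duration threshold. Related grade 3 diarrhoea/colitis of any duration therefore falls under the permanent stop.

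**2. The two rules by type of episode.** Section 5.5.1 speaks of treatment-related events and 7.1.1 of nivolumab-related ones, so the overlap is nivolumab-related episodes.

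| Nivolumab-related episode | 5.5.1 | 7.1.1 |
|---|---|---|
| Grade 3, 1 week or less | Stop permanently, off study | No discontinuation instruction |
| Grade 3, more than 1 week | Stop permanently, off study | Stop permanently |
| Grade 4 | Stop permanently, off study | Stop permanently |

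The sections differ in the first row only, and there 7.1.1 is silent; it does not grant permission.

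**3. Is precedence stated?** Section 5.5.1 settles the relation to Appendix D for hepatic events (an explicit override), for renal events (deferral) and for skin (its own note). No equivalent appears for GI events in the readable text. The cross-references to section 7 and Appendix D do not say which text prevails on discontinuation.

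**4. Patients covered by the wording.** The immune criteria in 7.1.1 sit under nivolumab given during chemoradiation. That means cohort 1 (8 patients) and cohort 3 (up to 12), from 16.2: 8 + 12 = 20, and 20/24 = 83%. Whether the text reaches cohort 2 is arguable. Within this group the issue arises only if doses are still planned. During chemoradiation it also needs an RT hold shorter than 7 consecutive days, because 6.2 removes the patient for a toxicity hold of 7 days or longer.

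**5. Effect on cohort decisions.** The toxicity criterion in 16.1.1 needs a grade 3 or higher event lasting at least 14 days. An episode of 1 week or less lasts at most 7 days, and 7 < 14, so it cannot count. The other criterion concerns completing chemoradiation within 8 weeks and does not refer to nivolumab discontinuation.

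**The case against.** The strongest reply is that no two instructions collide. Section 7.1.1 never says nivolumab may continue or resume after a short grade 3 episode, and a site that obeys 5.5.1 breaches nothing in 7.1.1. Section 5.5.1 is mandatory in wording, 7.1 is offered as suggestion, and 7.2 carries required toxicity stops forward from earlier sections. The drafters wrote down exceptions where they wanted them, and GI is not among them. This stands: 5.5.1 is the likelier governing rule, and a reader who infers that the protocol authorises re-challenge is going beyond the text.

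It is also fair that several safeguards lie between the wording and an actual re-dose. Nivolumab is held for suspected immune toxicity under either reading, and consultation with the coordinating group is suggested. Section 6.1 holds chemoradiation for grade 3 or higher GI toxicity until grade 1 or less, and nivolumab is skipped when cisplatin is held. These make the error less likely. They govern when a dose is held and do not settle whether nivolumab must stop for good.

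The Appendix D GI algorithm is a figure that is not shown. It may settle the short-episode case or may not, and nothing is inferred from its absence.

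What the reply does not answer is that the mandatory section itself directs the physician to section 7 before infusing, and says to follow it when the cause is unclear. A stated duration condition on a permanent-stop instruction, found at the place the reader is sent to, misleads in a way that mere silence would not.

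**Conclusion.** The point holds as an inconsistency by implication. Section 5.5.1 requires permanent discontinuation for related grade 3 diarrhoea/colitis of any duration; 7.1.1 attaches it only to nivolumab-related episodes lasting more than 1 week. A site relying on 7.1.1 could re-dose after a shorter episode. The correction is worth making because it concerns patient safety and costs almost nothing.

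Three stronger readings are tempting and are not supported:

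- **That up to 20 of 24 patients are at risk.** The figure counts patients to whom the wording most clearly applies. The documents give no rate of short related grade 3 episodes, so no number affected can be stated.
- **That the feasibility decisions are compromised.** Those in 16.1.1 are unaffected, as shown above.
- **That 7.1.1 wrongly delays IV steroids at grade 3.** The bullet does carry a 1-week steroid trigger, and grade 2 and grade 4 events receive steroids with no stated wait. Without the Appendix D figure no gap in steroid treatment can be asserted.

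The conclusion assumes that 5.5.1 expresses the sponsor's intention, which its wording and 7.2 support but no GI-specific sentence confirms.

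**What to change.** Split the grade 3 bullet in 7.1.1 in two.

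- **Discontinuation, with no duration condition:** *Discontinue nivolumab permanently for any related grade 3 diarrhoea/colitis, per 5.5.1, which governs discontinuation.*
- **Steroid treatment, as a separate sentence:** keep the existing trigger of more than 1 week unless the sponsor changes it after checking the Appendix D GI algorithm. The phrase should not simply be deleted, because it also sets when IV methylprednisolone starts; removing it outright would alter a treatment threshold.

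If the sponsor does intend re-challenge after short episodes, the place to say so is 5.5.1, as a listed grade 3 GI exception with its duration.

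The recommended change is to protocol wording only, with no effect on sample size, visits or analysis. Its one consequence is that patients with short related grade 3 episodes clearly come off nivolumab, as 5.5.1 already requires.
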